**SYNOPSIS: Intravital Microscopy (IVM) in patients with peritoneal carcinomatosis**

PI: [name] [name]

Co-PI: [name]

[name]

[name]

Statistician: [name], MS

Study Center: Mayo Clinic Florida

Concept and Rationale: Intravital microscopy (IVM) allows real-time, direct visualization of microscopic blood vessels and calculation of blood flow. Our group has used IVM in mouse models to characterize aberrant blood vessel structure surrounding tumor implants and the associated impaired lymphocyte trafficking along these tortuous vessels.[1] These preclinical studies have been translated to human intravital microscopy (HIVM) in a pilot study that analyzed the tumor-associated microvasculature at primary melanomas.[2] The feasibility of HIVM was 90% at the primary tumor. As an extension of this completed trial, [name] had implemented an on-going clinical trial (NCT02857374, Intravital Microscopy in Identifying Tumor Vessels in Patients with Stage IB-IIIC Melanoma Undergoing Sentinel Lymph Node Biopsy) that investigates the role of IVM in analyzing the vessels associated with sentinel lymph nodes. This proposed trial at Mayo Clinic Florida will further determine the usefulness of IVM in human subjects, now applying it to patients with deeper sites of tumor, i.e. peritoneal carcinomatosis.

In these clinical trials, fluorescein was used to augment visualization of tumor-associated vessels. It is a commonly used and safe intravital dye. Similarly, indocyanine green (ICG) is a commonly used dye and will be also used in this study. Due to its heavier molecular weight compared to fluorescein, ICG allows additional analysis of vessel permeability. Although it is also considered a safe intravital dye, small studies report a higher risk of adverse events (AEs) associated with its use in patients with hepatic or renal dysfunction.

In this clinical trial proposal, the following aims will be addressed:

1. Determine the feasibility of HIVM in characterizing the tumor-associated microvasculature in patients with peritoneal carcinomatosis.
2. To correlate these findings to the HIVM observations at the primary site, extent of carcinomatosis, tumor response, and survival outcomes.

**Objectives:**

*Primary objective(s):* To determine the feasibility of performing HIVM in patients with peritoneal carcinomatosis during standard course of treatment (cytoreductive surgery with

hyperthermic intraperitoneal chemotherapy, or CRS-HIPEC). A successful intravital microscopic observation will include the ability to complete each of the following:

1. Identify and measure vessels associated with peritoneal tumor implants
2. Determine vessel density per 10x field
3. Visualize vital dyes within the vessels [fluorescein and indocyanine green (ICG)]
4. Calculate the blood flow velocity of the vessels and tissue penetration of fluorescein and ICG as markers of vessel permeability.

*Secondary objective(s):*

1. Compare the microscopic observation of the tumor-associated vessels with normal tissue (peritoneal surface) in each individual subject.
2. Correlate the microscopic observations of the tumor-associated vessels with pathologic grade of tumor implants.
3. To correlate the microscopic observation of the microvasculature with tumor-specific and overall survival.

**Study Design:** This is a non-randomized, single center, study of HIVM observation in subjects with peritoneal carcinomatosis undergoing CRS-HIPEC.

All subjects will meet the inclusion and exclusion criteria prior to participation in this study. Standard evaluation by the Preoperative Anesthesia clinic at Mayo Clinic Florida may include additional testing such as EKG, chest x-ray, and/or pulmonary function tests.

The study will be performed in two parts. Part 1 will enroll 10 patients with an expected feasibility rate of 70%. Whereas the feasibility rate in primary melanoma was 90%, the expected feasibility rate for the peritoneal surface may be lower as the site is in an anatomically deeper location. If Part 1 is not met (i.e. in three or more patients), the primary objective would not be considered technically feasible, and then the study will be stopped. If Part 1 is fulfilled, then the study will continue with an additional 20 patients enrolled (total of 30 patients). Accrual is expected to take 2.5 years.

*Inclusion criteria:*

1. Age  $\geq$  18 years of age.
2. ECOG Performance Status of  $\leq 2$ .
3. Measurable tumor on the peritoneal surface by direct visualization requiring surgical resection in the OR.
4. Peritoneal carcinomatosis that meets indications for CRS-HIPEC. Sites of origin for tumor include appendix, colon, stomach, and primary peritoneal surface malignancies such as peritoneal mesothelioma.

5. Subject must understand the investigational nature of this study and sign an Independent Ethics Committee/Institutional Review Board approved written informed consent.
6. Subject must have a skin prick test pre-operatively (at the time of the preoperative visit and after signed informed consent for entry into this clinical trial is given) to determine any sensitivity to fluorescein.

*Exclusion criteria:*

1. Uncontrolled intercurrent illness including, but not limited to, ongoing or active infection, symptomatic congestive heart failure, unstable angina pectoris, cardiac arrhythmia, or psychiatric illness/social situations.
2. Renal dysfunction as defined as a GFR < 45.
3. Liver dysfunction as defined by Child-Pugh score > 5, or LFT's 1.5x above normal range.
4. Any known allergy or prior reaction to fluorescein or ICG or a positive skin prick test to fluorescein.
5. Pregnant or nursing female subjects, determined preoperatively with a urine pregnancy test.
6. Unwilling or unable to follow protocol requirements.
7. Any condition which in the Investigators' opinion deems the patient unsuitable (e.g., abnormal EKG).
8. Any condition that excludes CRS-HIPEC as the standard of care (e.g. high disease burden where alternative treatments like systemic chemotherapy would be preferred).

Primary and Secondary Endpoints/Criteria for Evaluation:

*Primary endpoint:* A patient will be deemed a success if each of the following parameters were measured:

1. Identify tumor implant associated vessels and measure vessel diameters
2. Determine vessel density per 10x field
3. Visualize vital dyes within the tumor-associated vessels (fluorescein and green ICG)
4. Calculate the blood flow velocity of the tumor-associated vessels and tissue penetration of fluorescein and ICG as markers of vessel permeability.

*Secondary endpoints:*

1. Post-operative comparison of the microvasculature of peritoneal carcinomatosis with normal tissue (peritoneum) in each individual subject using vessel diameters, vessel density, detection of intravital dye and flow rates.
2. Post-operative correlation of the microvasculature with pathologic features of the tumor implants (i.e. tumor grade) at the time of the final pathology report (5-7 days after surgery).
3. Post-operative correlation of the microscopic observation of the tumor microvasculature tumor-specific and overall survival.

**Subject Name:** \_\_\_\_\_

**Medical Record No.:** \_\_\_\_\_

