#### 3.3 PRIMARY AND SECONDARY ENDPOINTS:

*Primary endpoint:* A patient will be deemed a success if each of the following parameters were measured:

1. Identify tumor implant associated vessels and measure vessel diameters
2. Determine vessel density per 10x field
3. Visualize vital dyes within the tumor-associated vessels (fluorescein and green ICG)
4. Calculate the blood flow velocity of the tumor-associated vessels and tissue penetration of fluorescein and ICG as markers of vessel permeability.

*Secondary endpoints:*

1. Post-operative comparison of the microvasculature of peritoneal carcinomatosis with normal tissue (peritoneum) in each individual subject using vessel diameters, vessel density, detection of intravital dye and flow rates.
2. Post-operative correlation of the microvasculature with pathologic features of the tumor implants (i.e. tumor grade) at the time of the final pathology report (5-7 days after surgery).

3. Post-operative correlation of the microscopic observation of the tumor microvasculature tumor-specific and overall survival.

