Technical difficulties with the microscope apparatus (e.g. malfunction of the software or structural damage to any of the microscope components) or unforeseen events during the course of surgery that are unrelated to the study intervention but that result in the termination of the surgery (e.g. adverse reaction to anesthetic prior to administration of intravital dye or hemodynamic instability from a complication of the surgery) will not be considered failures of the primary objective. In these circumstances, the subject will be considered to be off-study and be replaced with a subsequent patient.

Off-line analysis of digitally recorded live video will be performed using parameters and statistical methods that have been developed in our preclinical imaging studies.[1] Lumenal cross-sectional diameter (D) of vessels and velocity (V) of dye labeled cells will be measured in off-line observations. Wall shear rate ( $\gamma$ ) will be calculated as  $8(V \div D)$ .[92] Vessel density will be determined by measuring the calculated blood vessel area as a percent of the total visual field area. If visible, the uptake of fluorescein or ICG will be measured as a diffusion rate (distance from tumor vessel over time) and as a percent of the total tumor field observed (percent of visual field expressed as surface area with dye detected). Blood flow velocity will be determined by the equation  $Q = (RBC \text{ velocity}/1.6) \times (d/2) \times \pi$ .

These data will be calculated and recorded in a spread sheet that will also be saved onto a password-protected hard drive in the Principal Investigator's laboratory. Additionally, all data will be de-identified and provided to the Biostatistician. Generated data and the raw video images will be stored for review at any time to satisfy any audit of the collected data. This saved data will readily allow the determination of a successful observation including the identification of tumor vessels, the associated vessel measurements, vessel density, and dye enhanced imaging acquisition.

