## 9 STATISTICAL METHODOLOGY

Initially ten patients will be treated to determine the feasibility of HIVM for peritoneal carcinomatosis. This first part of the study is a pilot study of feasibility. If seven or more patients are deemed a success by meeting all of the criteria below, then HIVM will be deemed feasible in the study of peritoneal carcinomatosis. Criteria include the ability to complete each of the following:

1. Identify and measure vessels associated with peritoneal tumor implants
2. Determine vessel density per 10x field
3. Visualize vital dyes within the vessels [fluorescein and indocyanine green (ICG)]
4. Calculate the blood flow velocity of the vessels and tissue penetration of fluorescein and ICG as markers of vessel permeability.

If the true success rate is 60%, the probability of deeming HIVM feasible is 63%; if the true success rate is 70%, then the probability of deeming HIVM feasible is 88%; and if the true success rate is 90%, then the probability of deeming HIVM feasible increases to 99%.

If HIVM is deemed feasible, then an additional 20 patients will be accrued to this study in order to address the following:

1. Post-operative comparison of the microvasculature of peritoneal carcinomatosis with normal tissue (peritoneum) in each individual subject using vessel diameters, vessel density, detection of intravital dye and flow rates.
2. Post-operative correlation of the microvasculature with pathologic features of the tumor implants (i.e. tumor grade) at the time of the final pathology report (5-7 days after surgery).
3. Post-operative correlation of the microscopic observation of the tumor microvasculature tumor-specific and overall survival.

An abnormal HIVM observation is defined by any of the following criteria:

1. Aberrant vessel structure compared to normal tissue, which includes tortuosity of the vessel wall or a closed loop formation.
2. Aberrant vessel branching patterns compared to normal tissue, which includes erratic and disorganized branching points.
3. Blood vessel density that is less than or greater than one standard deviation of the blood vessel density observed in normal tissue.
4. Inability to detect flow or intravital dye within a vessel.
5. Average blood flow rate through observed vessel that is less than one standard deviation of the average blood flow rate through a normal vessel.

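### The synopsis and Section 9 give opposite go/no-go decisions at exactly 7 successes in 10, the most likely result at the expected 70% rate

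*Combined protocol and SAP*

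**What the plan says.** The synopsis, under Study Design, sets the size and expectation of the first part: "Part 1 will enroll 10 patients with an expected feasibility rate of 70"%. It then gives the stopping condition, "If Part 1 is not met (i.e. in three or more patients), the primary objective would not be considered technically feasible", and the consequence, "and then the study will be stopped".

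Section 9 (Statistical Methodology) gives the rule from the success side: "If seven or more patients are deemed a success by meeting all of the criteria below, then HIVM will be deemed feasible". The consequence is that "If HIVM is deemed feasible, then an additional 20 patients will be accrued to this study". It prints the probability of declaring feasibility as 63%, 88% and 99% at true success rates of 60%, 70% and 90%; for the middle one, "if the true success rate is 70%, then the probability of deeming HIVM feasible is 88"%.

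Two other places fix how patients are counted. Section 3.3 makes the outcome all-or-nothing for each patient: "A patient will be deemed a success if each of the following parameters were measured". Section 4.2 says that equipment faults, and surgery ended by events unrelated to the study intervention, do not count as failures; in those cases "the subject will be considered to be off-study and be replaced with a subsequent patient".

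**The concern.** With a binary outcome and 10 evaluable patients, a rule on failures and a rule on successes must be complementary. Stopping at three or more failures is the complement of continuing at eight or more successes, not seven or more. The two statements therefore collide at 7 of 10.

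This is the only numerical go/no-go rule on the primary endpoint, and it controls 20 of the 30 planned patients. If 7 of 10 occurs, the choice between stopping and continuing would be made after the result is known, and each side could cite the protocol. The collision also falls on the result the design expects, since 7 of 10 is an observed rate of exactly 70%.

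**Working it through.** **Inputs.** n = 10 and expected rate 70% (synopsis, Study Design). Stop at three or more failures (same place, natural reading). Continue at seven or more successes (Section 9). Binary outcome (Section 3.3). Technical and unrelated losses replaced, so those losses do not change the denominator of 10 (Section 4.2).

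**Step 1. The two rules side by side.** Failures = 10 − successes.

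| Successes | Failures | Synopsis | Section 9 |
|---|---|---|---|
| 0 to 6 | 10 to 4 | stop | not feasible |
| 7 | 3 | **stop** | **feasible, continue** |
| 8 to 10 | 2 to 0 | continue | feasible, continue |

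**Step 2. Try to reproduce Section 9's printed probabilities.** With X binomial(10, p), P(X ≥ r) = Σ C(10, k) p^k (1 − p)^(10 − k) for k from r to 10.

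| Cut-off | p = 60% | p = 70% | p = 90% |
|---|---|---|---|
| Printed | 63% | 88% | 99% |
| ≥ 6 | 63.3% | 85.0% | 99.8% |
| ≥ 7 (Section 9) | 38.2% | 65.0% | 98.7% |
| ≥ 8 (synopsis) | 16.7% | 38.3% | 93.0% |

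Only the 99% reproduces under Section 9's own rule. The printed 63% is what a cut-off of six gives at 60%. The printed 88% is what a cut-off of seven gives at a true rate of 80% (87.9%), not 70%. None of the cut-offs from 4 to 10 returns all three figures, so they cannot show which rule was meant.

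**Step 3. Size of the conflict.** The rules differ only at X = 7, so the gap in the chance of continuing is P(X = 7) = 120 × p^7 × (1 − p)^3.

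At p = 0.7: 120 × 0.08235 × 0.027 = 0.2668. The neighbouring counts are P(X = 8) = 0.2335 and P(X = 6) = 0.2001, so 7 is the most likely count.

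| True rate | P(X = 7) | Continue, Section 9 (≥ 7) | Continue, synopsis (≥ 8) |
|---|---|---|---|
| 60% | 21.5% | 38.2% | 16.7% |
| 70% | 26.7% | 65.0% | 38.3% |
| 80% | 20.1% | 87.9% | 67.8% |
| 90% | 5.7% | 98.7% | 93.0% |

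**The case against.** The best reply is that there is one clear rule, in Section 9, and one badly built sentence in the synopsis. That sentence has no denominator and no word for failure, and its author may have meant more than three. The same paragraph expects 70% feasibility, which 7 of 10 meets exactly. The evidence on intent also leans towards Section 9: the printed 99% fits a cut-off of seven (98.7%) and not eight (93.0%), and none of the three printed figures fits eight. A cut-off of eight would stop the study 61.7% of the time (100 − 38.3) at the expected rate. The conflict touches one count out of eleven, and Section 8 gives the monitoring board an annual review with power to recommend termination.

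Much of this stands. A slip in the synopsis is the likelier explanation. The wrong probabilities are a distinct error: they would need correcting even if the synopsis agreed with Section 9. But likelihood of intent is not a statement of precedence, and the document contains none. The natural reading of the synopsis counts patients in whom the objective was not met; the alternative, that three successes suffice, fits neither the 70% expectation nor Section 9. The single disputed count is the most probable one at the design rate, and the board's review supplies no numerical threshold to settle it.

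**Conclusion.** The concern holds. The synopsis and Section 9 prescribe opposite actions at 7 of 10, and no text resolves them. The result has a probability of 26.7% at the expected 70% rate and of 5.7% to 26.7% across true rates of 60%, 70%, 80% and 90%. Section 9's 63% and 88% belong to neither rule at the true rates stated.

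This rests on three assumptions: the synopsis phrase counts patients who fail; Part I is judged on 10 evaluable patients, as the replacement provision in Section 4.2 implies; and patients are independent with a common success probability. The contradiction itself needs only the first two. The third affects only the probabilities. Because the defect lies in the decision threshold for the primary endpoint, it must be fixed.

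**What to change.** State one cut-off in both places, in matching terms of successes and failures out of 10 evaluable patients, and recalculate Section 9's probabilities for it.

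- **Option A, keep Section 9's rule.** Change the synopsis so that the study stops if the criteria are not met in four or more of the 10 patients, that is, with fewer than seven successes. Replace 63%, 88% and 99% with 38%, 65% and 99% at true rates of 60%, 70% and 90%.
- **Option B, keep three failures as the stopping point.** Change Section 9 to eight or more successes and replace the probabilities with 17%, 38% and 93%.

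The indirect evidence favours Option A, but the sponsor must say which was intended, and should do so before the Part I result is known.

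The cost is a short text correction in the synopsis and Section 9 (Option A) or in Section 9 alone (Option B). The Part I sample size and the procedures do not change. The stated chance of continuing at a true rate of 70% falls from the printed 88% to 65% under Option A or 38% under Option B; the sponsor should confirm that it accepts the corrected figure.

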**Title: Intravital Microscopy (IVM) in patients with peritoneal carcinomatosis**

INCLUSION CRITERIA				
Y	N	N/A	All answers must be “YES or “N/A” for subject enrollment.	Date
			1. Age $\geq$ 18 years of age.	
			2. Have an ECOG Performance Status of $\leq$ 2. Refer to Appendix C.	
			3. Have measurable disease in the peritoneum by direct visualization (visible lesion typically $> 0.5$ cm in maximal diameter).	
			4. Carcinomatosis that meets indications for CRS-HIPEC.	
			5. Subject must understand the investigational nature of this study and sign an Independent Ethics Committee/Institutional Review Board approved written informed consent form prior to receiving any study related procedure.	
			6. A negative skin-prick test to fluorescein.	

EXCLUSION CRITERIA				
Y	N	N/A	All answers must be “NO” or “N/A” for subject enrollment	Date
			1. Uncontrolled intercurrent illness including, but not limited to, ongoing or active infection, symptomatic congestive heart failure, unstable angina pectoris, cardiac arrhythmia, or psychiatric illness/social situations.	
			2. Renal dysfunction as defined as a GFR $< 45$ .	
			3. Liver dysfunction as defined by Child-Pugh score $> 5$ , or LFT's 1.5x above normal range.	
			4. Any known allergy or prior reaction to fluorescein or ICG or a positive skin prick test to fluorescein.	
			5. Pregnant or nursing female subjects, determined preoperatively with a urine pregnancy test.	
			6. Unwilling or unable to follow protocol requirements.	
			7. Any condition which in the Investigators' opinion deems the patient unsuitable (e.g., abnormal EKG).	
			8. Any condition that excludes CRS-HIPEC as the standard of care for the patient.	

## 1 BACKGROUND

Intravital microscopy (IVM) is the microscopic observation of living tissue in real time. IVM has been successfully applied to the investigation of the tumor microvasculature of human primary melanoma.[3] It has been shown that tumor vessels lack the sequential hierarchy of normal vessels such that arterioles, capillaries, and venules typically cannot be discriminated within tumor tissues.[4, 5] This disorganization of aberrant tumor vessels was demonstrated in a previous feasibility clinical trial.[2] These tumor-associated vessels were characterized by irregular diameters, aberrant branching patterns, abnormal blood flow rates, and anastomotic structures. More specifically, the human tumor-associated vessel diameters observed in real time *in vivo* were larger than those predicted either by *in vivo* mouse models or by human immunohistochemistry (IHC) on tumor specimens analyzed *ex vivo*.[3] These characteristics could have profound influence on the delivery of agents (i.e., chemotherapy or cellular immunotherapy) to the tumor microenvironment.[6]

In order to obtain this data, human intravital microscopy (HIVM) was used first in melanoma primary tumors. Intravital microscopy (IVM) has also been used to directly examine the hemodynamic properties of tumor microvessels in preclinical mouse models.[1, 7-9] These studies were primarily based on the analysis of blood vessels and leukocytes labeled *in situ* with fluorescent tracking dyes (e.g., fluorescein or ICG). Recent mouse studies in B16 murine melanoma have used IVM to demonstrate that the abnormal, tortuous vascular structure in tumors represents a bottleneck to adoptive cell transfer immunotherapy because of poor trafficking of cytotoxic effector T cells at this site.[1] Others have used different forms of IVM to observe lymphatics or metastatic disease in real time in mouse models.[10, 11] There has also been reported real time imaging of human tumor and lymphatics using different techniques such as multiphoton imaging, high resolution ultrasound, or optical coherence tomography.[12, 13] To date, there have been no studies of IVM in the setting of human peritoneal carcinomatosis.

The detection of blood flow parameters (including vessel diameter, flow rates, vessel density, and fluorescent markers of tissue diffusion) in tumor implants of patients with peritoneal carcinomatosis may have utility in characterizing the locoregional spread of disease and in predicting drug uptake and clinical response in these tumor implants. The overall goal will be to characterize, for the first time, vasculature associated with peritoneal carcinomatosis in real-time. It is anticipated that this novel approach has the potential to generate a more complete picture of the tumor-associated locoregional vasculature. The investigation of tumor-associated vessels in real time may lead to a better understanding of factors influencing systemic drug efficacy.

